**01-03-2018**

**Unique Protocol ID: IRB 2017-215**

**NCT03404700**

## **Summary**

Eggs are nutrient dense, convenient, affordable, and provide key macro and micronutrients in one's diet. Despite having a lot of benefits of consuming eggs in relation to health recent epidemiological studies raise health concerns about egg intake for subgroups of people. For instance, under free-living conditions, higher egg intake is associated with increased cardiovascular disease (CVD) risk in diabetic individuals as well as increased risk of developing type 2 diabetes. However, these studies do not establish that egg consumption "causes" health issues.

It is also possible that the association of egg intake with increased CVD risk in diabetics, or with a greater risk of developing diabetes, is simply due to the other foods that people usually eat with eggs, such as saturated fats, and not due to eggs *per se*.

For part I, the investigators propose to test this hypothesis by determining the food intake of 48 non-diabetic individuals under free-living conditions using the remote food photography method (RFPM), which uses smartphone technology. The frequency of egg consumption will be obtained using a food frequency questionnaire (FFQ). In addition, participants will record their food intake using food record diary and a 24-hour food recall method. Energy intake information gathered from RFPM will be compared with the 7-day food record and the 24-hour recall.

Next, for part II, the same study participants will be offered four separate test breakfasts of similar calories, containing 1) Eggs; 2) Eggs with a high amount of saturated fat; 3) Cereal breakfast (neither eggs nor saturated fat); or 4) Cereal breakfast with a high amount of saturated fat. Alteration of blood glucose, insulin, hunger, and satiety hormones (ghrelin, PYY, GLP-1), and metabolic rate will be measured before and after each breakfast in part II.

The investigators expect to determine if the purported association of eggs to alterations in glucose control and related metabolic alterations are independent of eggs, but mainly due to saturated fat is eaten along with eggs rather than the egg consumption itself.

### **A. Specific Aims/ Objectives:**

1. To use the RFPM to accurately determine the dietary pattern associated with egg intake in 48 free living non-diabetic individuals who eat eggs often.

2. To assess and compare the hormonal levels related to hunger and satiety following; A-Egg breakfast, B-Eggs breakfast with high amount of saturated fat, C- Cereal breakfast, D- Cereal breakfast with high amount of saturated fat.
3. To assess and compare insulin levels and blood glucose levels following A-Egg breakfast, B-Eggs breakfast with high amount of saturated fat, C- Cereal breakfast, D-Cereal breakfast with high amount of saturated fat.
4. To examine whether total energy intake and consumption of saturated fat will be associated with the baseline insulin levels, blood glucose levels, Homeostatic Model Assessment (HOMA) index of insulin resistance calculated using glucose and insulin levels, and HbA1C levels.
5. To compare diet induced thermogenesis in A-Egg breakfast, B-Eggs breakfast with high amount of saturated fat, C- Cereal breakfast, D-Cereal breakfast with high amount of saturated fat.
6. To compare RFPM method with 7-day food record and 24-hour recall in dietary assessment

## **B. Hypotheses:**

These aims will test the following hypotheses:

1. Meals that include eggs will have higher energy and saturated fat contents as determined by RFPM, compared to corresponding meals (i.e. breakfast, lunch, or dinner) without eggs.
2. As determined by RFPM, individuals of the study sample who will be in the highest quartile in terms of egg consumption in the free-living condition (defined as high egg consumers) will have a higher intake of saturated fat and total energy as compared to individuals who will be in the lowest quartile in terms of egg consumption (defined as low egg consumers).
3. Baseline insulin level, blood glucose level, the Homeostatic Model Assessment (HOMA) index of insulin resistance using fasting glucose and insulin levels, and HbA1C will be positively associated with total EI and saturated fat intake determined by RFPM, even when adjusted for age, sex, BMI and waist circumference
4. Above outcome variables will not be associated with egg intake determined by RFPM.

5. In the randomized partial crossover study, presence of eggs in the breakfast will be associated with a) a greater increase (i.e. both area under the curve and pre-post change) in satiety hormones (i.e. PYY and GLP-1), b) a less profound increase in blood glucose and insulin levels, c) a greater decrease in the hunger hormone (ghrelin) and d) an increase in the area under the curve of metabolic rate when controlled for the content of saturated fat in the test diets.
6. In the randomized partial crossover study, presence of a high amount of saturated fat in the breakfast will be associated with a) a greater increase (i.e. both area under the curve and pre-post change) in satiety hormones (i.e. PYY and GLP-1), b) a less profound increase in blood glucose and insulin levels, c) a greater decrease in the hunger hormone (ghrelin) and d) an increase in the area under the curve of metabolic rate when controlled for the presence of eggs in the test diets.
7. In the randomized partial crossover study, the associations mentioned in hypothesis 5 will be moderated by the presence of a high amount of saturated fat in the diet.
8. Estimates of total EI by RFPM will be significantly greater than EI estimates by 7-day food record and the 24-hour recall in dietary assessment.

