### **C. Significance:**

An association between egg consumption and diabetes should not be ignored. However, it is important to identify if such an association does indeed exist and, if so, whether or not there is evidence that suggests that it is not the eggs themselves that drive the association, but rather a concurrent undesirable profile of macronutrient intake. Food intake data assessed by subjective recall methods are highly questionable due to potential inaccuracies . Capturing food intake data in real time by RFPM is the greatest strength of this project. The RFPM has been validated for accuracy against the doubly labeled water method . With high accuracy, we will identify the nutrients associated with egg consumption. Intake at every meal will be captured for 7 days in a free-living population, which eliminates the reporting bias around subjective measures of food intake and provides greater fidelity of reporting usual diet. This will help in better understanding the health effects that are currently ascribed to eggs by epidemiological studies using dietary recall methods. We expect that this study will demonstrate that intake of eggs is associated with an undesirable profile of macronutrient intake. By doing measuring blood

glucose, insulin levels following four tests breakfast that include eggs and saturated fats we will be able to measure the acute effects of egg based diet and influence of saturated fats to glycemic status. In addition, by doing hunger and satiety hormones will enable to explain the changes that coexist with insulin and glucose alterations. RMR will give indirect measurement of fed state. Overall, the studies will provide stronger evidence to accept or refute some of the adverse effects reportedly associated with egg consumption, so that appropriate dietary recommendations could be designed. It will form the basis for future research to determine if the dietary pattern accompanying eggs and not eggs per se is linked to diabetes and other adverse metabolic consequences.

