## **Study Design and Methods**

### **I. Subjects:**

#### **A. Overview:**

The proposed study will comprise of two parts: Part I: an observational study based on ecological momentary assessment, and Part II: a randomized partial crossover clinical trial. Same subjects will participate in both parts of the study.

In the observational study, the dietary intake of the subjects will be evaluated using an ecological momentary assessment approach for 7 days. In the randomized partial crossover clinical trial, four test breakfasts will be administered so that each subject will get exposed to only two out of the four diets (thus, partial crossover). Therefore, there will be six possible combinations of diets (i.e.  $4! / 2! [4-2]!$ ) and 12 possible ordered combinations (i.e. permutations;  $4! / [4-2]!$ ) of diets. Four subjects will be randomly assigned to each of these 12 possible ordered combinations of diets. Thus, the total sample size will be 48 (i.e.  $n = 4 \times 12$ ).

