**Statistical Analyses Plan (SAP):**

Data will be imported to R statistical software and the distributions will be examined visually to make a decision about the appropriate statistical tests (i.e. parametric / non-parametric) to be used for all comparisons. All statistical analyses will be conducted using R statistical software. Family-wise error rate will be maintained at 0.05.

Free living EI and saturated fat intake during main three meals (i.e. breakfast, lunch and dinner) of each subject will be determined using RFPM and the meals of all test subjects will be categorized based on the presence or the absence of eggs in the meals. Means of EI and saturated fat intake during each main meal will be compared between the two categories (i.e. eggs present vs. eggs absent) using multi-level mixed-effects regression models constructed using the lmerTest package in R statistical software. Age, sex, baseline BMI and / or waist circumference will be included in the models as subject-level covariates.

Based on RFPM data, mean EI and saturated fat intake of the high egg consumers (i.e. individuals in the top quartile based on egg consumption) will be compared with the mean EI and saturated fat intake of the low egg consumers (i.e. individuals in the bottom quartile based on egg consumption) via Welch t-tests or the Wilcoxon test, depending on the distributions of the data.

Linear regression models will be constructed to examined the associations between a) total EI, b) saturated fat intake and c) egg intake and each of i) baseline insulin level, ii) blood glucose level, iii) HOMA-IR, and iv) HbA1C level. The usual regression assumptions will be assessed and any concerns will be ameliorated as appropriate (e.g. apply a transformation as guided by Box-Cox)

Using the data obtained in the randomized partial crossover trial, multi-level mixed effects regression models will be constructed using the lmerTest package in R statistical software to predict each of a) PYY (AUC and pre-post change); b) GLP-1 (AUC and pre-post change); c) ghrelin (AUC and pre-post change); d) blood glucose (AUC and pre-post change); e) insulin (AUC and pre-post change); f) metabolic rate using i) the presence of eggs in the diet; ii) the

presence of a high content of saturated fat in the diet; iii) their interaction. Age, sex, baseline BMI and / or waist circumference will be included in the models as subject-level covariates.

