**Statistical procedures:**

**a. Power calculations:** With 40 subjects, we will be at least 80% powered to detect effect sizes that are equal to or greater than 0.45, which is a fairly modest effect size, using a nominal value of 0.05 for the level of each test. We will similarly be powered to detect a correlation with magnitude of at least 0.43; see Figure 1. With conservative adjustment for multiple comparisons, these thresholds rise to 0.61 and 0.53, respectively; see Figure 2.

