**Figure 1:**

**Figure 2:**

**b. Analyses:**

- Within-subject comparison of meals that include eggs vs similar meals (e.g. breakfast vs breakfasts) without eggs for energy and saturated fat content.
- Comparison of daily energy and saturated fat intakes between low and high egg consumers (top quartile vs bottom quartile as determined by FFQ). Because this measure of egg consumption is

based on self-reported FFQ recall, as a sensitivity analysis we will also consider the correlations between these outcomes and observed egg consumption over the period of observation.

iii. Correlation between HbA1C or fasting glucose levels and total energy intake or saturated fat intake (for 7 days), with and without adjustment for age, BMI, energy and saturated fat intake.

**Expected results:** We expect that meals, particularly breakfasts, that include eggs have higher energy and saturated fat content due to accompanying foods (such as hash browns, fries, sausages, or bacon). This may further contribute to greater overall energy and saturated fat intake for high egg consumers vs those who consume eggs less frequently. Finally, we anticipate that when adjusted for age, BMI, energy and saturated fat intake, fasting blood glucose or HbA1c will not be significantly associated with egg intake.

**Implications:** we expect that the purported association of eggs to dysregulated glycemic control is independent of eggs, but mainly due to the dietary pattern around egg intake. If true, an informational campaign will be needed to clear eggs from the “guilt by association”. However, if egg intake is indeed associated with impaired glycemic control, then appropriate steps should be taken to inform people accordingly.

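### Hypothesis 4 predicts no association between egg intake and baseline glycaemia, but the plan gives no margin or interval rule, and 48 subjects cannot reliably exclude a moderate association

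*Combined protocol and SAP*

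**What the plan says.** Under B. Hypotheses, Hypothesis 3 predicts that baseline insulin, glucose, HOMA-IR and HbA1c are positively associated with energy and saturated fat intake, after adjustment for age, sex, BMI and waist circumference. Hypothesis 4 then predicts the opposite for eggs: "Above outcome variables will not be associated with egg intake determined by RFPM".

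The matching analysis in the Statistical Analyses Plan is: "Linear regression models will be constructed to examined the associations between a) total EI, b) saturated fat intake and c) egg intake", each against the four baseline measures. That paragraph covers regression assumptions and transformations. It says nothing about a margin, an equivalence test or how an interval would be read. The SAP also holds family-wise error at 0.05, without naming the family or the method.

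The sample size comes from the crossover layout in A. Overview, four subjects in each of 12 diet orders: "Thus, the total sample size will be 48". The only power statement is in the appended 40-subject proposal, under a. Power calculations, and it concerns detection: "We will similarly be powered to detect a correlation with magnitude of at least 0.43". With a multiplicity adjustment that threshold rises to 0.53.

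On interpretation, C. Significance of the current protocol says that "the studies will provide stronger evidence to accept or refute some of the adverse effects reportedly associated with egg consumption". The appended proposal is more direct. Its expected result is that "fasting blood glucose or HbA1c will not be significantly associated with egg intake", and its implications paragraph continues: "If true, an informational campaign will be needed to clear eggs from the" charge of guilt by association.

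**The concern.** A regression test can give evidence for an association. Failing to reject does not give evidence against one unless the estimate is precise enough to rule out associations that matter. Hypothesis 4 is a prediction of absence, and the plan supplies no criterion that would make absence demonstrable. A coefficient that is non-significant because the study is small would look the same as one that is non-significant because eggs are unrelated to glycaemia.

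Multiplicity control works in the wrong direction here. A stricter threshold protects against false positives, but for a predicted null it makes apparent support easier to obtain.

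At stake is how Part I is reported. The Summary of the current protocol expects to separate eggs from the saturated fat eaten with them, and Hypothesis 4 is the part of that contrast that concerns habitual egg intake and baseline glycaemia. Imprecision alone could appear to confirm it.

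**Working it through.** **Inputs.** n = 48 (A. Overview), all assumed complete. Two-sided 0.05 per test; the documents do not state sidedness, but step 1 shows that two-sided reproduces their figure. Covariates k = 0 or k = 4 (age, sex, BMI and waist, as named in Hypothesis 3; the SAP regression paragraph names none). True correlations of 0.20 and 0.30 are assumptions, because the documents give no association of concern. Method: Fisher z with standard error 1/√(n − 3 − k).

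**1. The documents' own figure.** At n = 40 and 80% power, r = tanh[(1.960 + 0.842)/√37] = tanh(0.461) = 0.431. This matches the stated 0.43. A one-sided test would give 0.387. The same formula at n = 48 gives 0.395 (k = 0) or 0.412 (k = 4).

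**2. Precision at n = 48.** 95% limits around an observed correlation of 0:
- k = 0: tanh(1.96/√45) = 0.284
- k = 4: tanh(1.96/√41) = 0.297

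An observed correlation of 0.20 would be non-significant, yet its upper limit is tanh(0.203 + 0.292) = 0.46 (k = 0).

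**3. Chance of non-significance, one outcome.** This is Φ(1.96 − δ) − Φ(−1.96 − δ), with δ = atanh(r)·√(45 − k).

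| True r | δ, k = 0 | Non-significant | δ, k = 4 | Non-significant |
|---|---|---|---|---|
| 0.30 | 0.310 × 6.708 = 2.08 | 45% | 0.310 × 6.403 = 1.98 | 49% |
| 0.20 | 0.203 × 6.708 = 1.36 | 73% | 0.203 × 6.403 = 1.30 | 75% |

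Bonferroni over four outcomes (0.0125 each, an illustrative choice) raises the r = 0.30 figure to 66% (k = 0) or 70% (k = 4).

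**4. Chance that all four outcomes are non-significant.** Hypothesis 4 covers four outcomes measured in the same people, so step 3 does not describe the whole hypothesis. Simulating 48 subjects with egg intake correlated 0.30 with each outcome, and a common correlation among outcomes of 0.3 to 0.9 (assumed), gives:
- nominal 0.05: about 9% to 31%
- Bonferroni over four tests: about 28% to 53%

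If egg intake is related to only some of the outcomes, these figures are higher.

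**5. What a formal margin would require.** Take two one-sided tests at 0.05 each, a true correlation of 0, and an assumed margin. For a margin of 0.30, power at n = 48 is 33% (26% with k = 4), and 80% power would need n = 93. For a margin of 0.43, power at n = 48 is 85%. Under the stricter rule that the 95% CI must lie inside ±0.30, the chance is 2Φ(0.310 × 6.708 − 1.96) − 1 = 9% (2% with k = 4).

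**The case against.** The strongest reply has four parts.

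- **No decision rule is written.** The SAP says the regressions will examine associations. It nowhere says that p above 0.05 counts as support, and regression output includes intervals that could be reported. This is correct. A reader might infer that the current plan explicitly equates non-significance with clearing eggs, but that wording is in the appended 40-subject proposal, which has a different design and also says what should follow if eggs do prove to be associated. The current protocol implies the reading less directly. The gap remains, because nothing commits the sponsor to read the intervals.
- **A moderate association is not always beyond exclusion.** An estimate almost exactly at zero has limits that just exclude 0.30 when no covariates or four are used, and the study has good power to exclude 0.43. A claim that the design cannot exclude a moderate association would therefore be too strong; it cannot do so reliably.
- **The 45% figure is per outcome.** A reader might take it as the chance that Hypothesis 4 is upheld at r = 0.30. Read as requiring all four nulls, that chance is lower, as step 4 shows, but not negligible.
- **Hypothesis 4 is not the study's headline.** None of the six primary outcomes is this association, Aim 4 names only energy and saturated fat, and the randomised breakfasts test eggs through a directional hypothesis that imprecision cannot confirm. This stands and lowers the severity.

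A reader might also infer that the entry criteria (no diabetes, at least one egg a week) and the 7-day window bias the result towards a null. They may attenuate an association, but the documents do not quantify this, and the BMI, age and egg-intake ranges remain wide. The point does not depend on it.

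**Conclusion.** The concern holds as a should-fix. Hypothesis 4 is a claim of absence with no criterion that could establish absence, and 48 subjects cannot reliably exclude a moderate association. The single-outcome figures rest on the Fisher approximation, two-sided 0.05 and 48 complete cases; any dropout makes them worse. The joint figures also rest on an assumed r of 0.30 with every outcome and an assumed common correlation among outcomes, neither of which is in the documents. Changing these assumptions changes the size of the problem. It does not supply the missing criterion.

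**What to change.** Reword Hypothesis 4 and the SAP regression paragraph along these lines:

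> The association of egg intake with each baseline glycaemic outcome will be reported as an estimate with its 95% confidence interval. Hypothesis 4 is exploratory. With 48 subjects the interval for a correlation near 0 is about ±0.28 to ±0.30. A non-significant coefficient will not be reported as absence of association, or as evidence that eggs are not linked to glycaemia.

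If the sponsor wants a confirmatory statement of no association, it should set and justify a margin before seeing the data, and call the result inconclusive whenever the interval crosses that margin. Step 5 shows that at n = 48 a margin of 0.30 would seldom be met even if the true correlation were 0.

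The cost is wording only, with no added subjects or procedures. The drawback is that Hypothesis 4 will probably be reported as inconclusive, which is less favourable than a statement of no association.

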### **C. Significance:**

An association between egg consumption and diabetes should not be ignored. However, it is important to identify if such an association does indeed exist and, if so, whether or not there is evidence that suggests that it is not the eggs themselves that drive the association, but rather a concurrent undesirable profile of macronutrient intake. Food intake data assessed by subjective recall methods are highly questionable due to potential inaccuracies . Capturing food intake data in real time by RFPM is the greatest strength of this project. The RFPM has been validated for accuracy against the doubly labeled water method . With high accuracy, we will identify the nutrients associated with egg consumption. Intake at every meal will be captured for 7 days in a free-living population, which eliminates the reporting bias around subjective measures of food intake and provides greater fidelity of reporting usual diet. This will help in better understanding the health effects that are currently ascribed to eggs by epidemiological studies using dietary recall methods. We expect that this study will demonstrate that intake of eggs is associated with an undesirable profile of macronutrient intake. By doing measuring blood

glucose, insulin levels following four tests breakfast that include eggs and saturated fats we will be able to measure the acute effects of egg based diet and influence of saturated fats to glycemic status. In addition, by doing hunger and satiety hormones will enable to explain the changes that coexist with insulin and glucose alterations. RMR will give indirect measurement of fed state. Overall, the studies will provide stronger evidence to accept or refute some of the adverse effects reportedly associated with egg consumption, so that appropriate dietary recommendations could be designed. It will form the basis for future research to determine if the dietary pattern accompanying eggs and not eggs per se is linked to diabetes and other adverse metabolic consequences.

